5.5 Analysis Populations

The population defined for analysis will include the intent-to-treat (ITT), safety population, and the per protocol (PP) population.

5.5.1 Intent-To-Treat Population

The ITT population will include all subjects who were randomized, received the study device or underwent neurectomy, and completed at least one post-baseline assessment of efficacy. Subjects will be analyzed in the group to which they were randomized. The ITT population will be used for analyses of accountability, demographics, efficacy (superiority testing), and the calculation of the 95% confidence interval about the mean VAS change in the Axoguard® Nerve Cap group for the testing of the null hypothesis H_{0B}.

5.5.2 Safety Population

The safety population will include all subjects who had the study device inserted. This population will be used for all safety analyses.

5.5.3 Per Protocol Population

The Per Protocol population will include all subjects in the ITT population who have no major protocol violations

This population will be the primary analysis population for the test of non-inferiority using the difference between repair types.

5.6 Planned Analyses

A final analysis is planned after the last subject completes or discontinues the study, and the resulting clinical database has been cleaned, quality checked, and locked. The pilot phase data will be included along with the comparative phase data in the final data analyses.

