3.8 Randomization (comparative phase only)

In the pilot phase, the initial 15 subjects in will be assigned to open label treatment with Axoguard® Nerve Cap. In the subsequent comparative phase, subjects will be centrally randomized using an Interactive Web Response System (IWRS), OpenClinica, to undergo either neurectomy or implantation of the Axoguard® Nerve Cap in a ratio of 1:1. Only subjects meeting all inclusion and exclusion criteria shall be randomized.

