5. STATISTICAL CONSIDERATIONS

Descriptive statistical methods will be used to summarize the data from this study. Unless stated otherwise, the term "descriptive statistics" refers to number of events (n), mean, median, standard deviation (SD), standard error, minimum, maximum, and coefficient of variation (CV) for continuous data and frequencies and percentages for categorical data. All data collected during the study will be included in data listings. Unless otherwise noted, the data will be sorted by subject number, and then by date within each subject number.

Unless specified otherwise, all statistical testing will be two-sided and will be performed using an overall significance (alpha) level of 0.05.

All statistical analyses will be conducted with the SAS® System, version 9.1.3 or higher.

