7.1. Sample Size and Power

A total of 101 participants (15 pilot; 86 comparative/randomized) at up to 20 sites will be enrolled.

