7.2. Randomization and Masking

For the comparative study, participants will be centrally randomized 1:1 to one of two treatment groups – neurectomy plus Axoguard Nerve Cap or neurectomy alone – in accordance with a computer-generated randomization schedule to achieve a total of 86 target repairs.

For participants presenting with multiple neuromas during randomization to treatment, multiple neuromas may be included in the study. The primary neuroma will be identified by the investigator prior to randomization. This repair will be utilized for all analyses. Additional (secondary) treated neuromas must meet the same inclusion/exclusion criteria and receive the same treatment (as randomized: Axoguard Nerve Cap or Neurectomy). Whether being treated for

one or multiple neuromas, the acceptability for either treatment shall be decided prior to randomization of the participant.

While blinding the surgeon to treatment is not possible, blinding the participant is possible and all efforts should be taken to preserve this blind. Randomization will be used to assign the participant to a treatment group intra-operatively. Therefore, the participant will be blinded to the treatment used. Direct verbal or written communication regarding treatment identification beyond what is required at an institution for recording the surgical procedures is prohibited.

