8.1. General

Data collected from each study part will be analyzed separately. Descriptive statistical methods will be used to summarize the data from this study. Unless stated otherwise, the term "descriptive statistics" refers to number of events (n), mean, median, standard deviation (SD), interquartile range (IQR), minimum, and maximum for continuous data and frequencies and percentages for categorical data.

The term 'treatment group' refers to the type of procedure conducted, either Axoguard Nerve Cap (AXOG) or Neurectomy (NEUR). All statistical analyses will be conducted with validated statistical software package like SAS or Stata.

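### Protocol 5.6 brings the open-label pilot data into the final analyses without limit, against SAP 8.1 and the Protocol's own ITT and PP sets; the clearest exposure is the safety comparison

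*Protocol*

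**What the plan says.** On combining the phases, Protocol 5.6 (Planned Analyses) says "The pilot phase data will be included along with the comparative phase data in the final data analyses". It names no endpoint, population or test, and does not restrict the inclusion to description. SAP 8.1 (General) says "Data collected from each study part will be analyzed separately".

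On who the pilot subjects are, Protocol 3.8 says "In the pilot phase, the initial 15 subjects in will be assigned to open label treatment with Axoguard® Nerve Cap". Only the later cohort is allocated by chance: under SAP 7.2, "participants will be centrally randomized 1:1 to one of two treatment groups". SAP 7.1 gives the numbers: "A total of 101 participants (15 pilot; 86 comparative/randomized) at up to 20 sites will be enrolled".

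On efficacy populations, Protocol 5.5.1 requires randomisation for ITT, which serves superiority. Protocol 5.5.3 makes the per-protocol set, used for non-inferiority, a subset of ITT. SAP 7.4.1 defines pilot and comparative ITT sets separately. SAP 9.1.2 gives the pilot primary endpoint descriptive statistics only and places the tests in the comparative study.

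On safety, Protocol 5.5.2 says "The safety population will include all subjects who had the study device inserted", and uses that set for every safety analysis. Protocol 5.9 compares adverse events between treatment groups, and Protocol 5.10 makes the absence of a clinically significant difference in product-related event rates part of study success. SAP 7.4.4 defines one safety set spanning both phases and adds the neurectomy subjects.

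**The concern.** An analyst cannot follow both sentences for any between-group result. Protocol 5.2 looks to the SAP for the technical detail, but neither document says which prevails in a conflict. The Protocol is also at odds with itself, since the populations in 5.5.1 and 5.5.3 cannot contain the subjects that 5.6 brings in. Protocol 5.7.1 adds to this: it justifies the absence of a type I error adjustment by describing the final analysis as one of blinded group data, which a single-arm, open-label cohort does not fit.

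The direction of entry matters. Pilot subjects can join only the cap arm. They know their treatment, were enrolled before the randomised cohort and have no concurrent controls, while the primary outcome is a self-marked pain scale. Any difference between phases in expectation, calendar time or surgical experience would be counted as a device effect. If the choice stays open until the data are available, the reported cap group could be 43 or 58 depending on which sentence is followed.

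**Working it through.** **Inputs.** Pilot 15 and randomised 86 (SAP 7.1); 1:1 allocation (SAP 7.2); two-sided 0.05 (Protocol section 5). The 14-20 mm minimum clinically significant VAS reduction (Protocol 1.1) is used only for scale. The available text gives no SD and no expected pilot-versus-randomised shift, so both are assumed below and shown over a range. Full enrolment and treatment as allocated are also assumed.

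**The plan's own figure.** 15 + 86 = 101, which reproduces the stated total. 86 / 2 = 43 per randomised arm.

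**Group composition under each reading.**
- SAP 8.1: 43 v 43, all randomised.
- Protocol 5.6 taken literally: 43 + 15 = 58 v 43. The non-randomised share of the cap arm is 15 / 58 = 0.259, or 26%.

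**Bias if pooled.** If pilot subjects differ systematically from randomised cap subjects by b mm, the unadjusted cap mean, and so the difference, moves by (15/58) × b:
- b = 5: 0.259 × 5 = 1.3 mm
- b = 10: 0.259 × 10 = 2.6 mm
- b = 14: 0.259 × 14 = 3.6 mm
- b = 20: 0.259 × 20 = 5.2 mm

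A negative b gives the same sizes in the other direction.

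**Two-sided type I error of a single pooled test.** Normal approximation, SE = SD × √(1/58 + 1/43), with the test statistic displaced by bias / SE. For example, at SD 25 and b = 10, SE = 25 × 0.2012 = 5.03 and the displacement is 2.59 / 5.03 = 0.51, giving 0.081.

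| Assumed SD (mm) | b = 0 | b = 5 | b = 10 | b = 14 | b = 20 |
|---|---|---|---|---|---|
| 20 | 0.05 | 0.062 | 0.099 | 0.147 | 0.251 |
| 25 | 0.05 | 0.058 | 0.081 | 0.111 | 0.177 |
| 30 | 0.05 | 0.055 | 0.071 | 0.092 | 0.137 |

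**What pooling would buy.** The SE ratio is √(1/58 + 1/43) / √(2/43) = 0.933, a fall of 6.7%. At SD 25, power for 14 mm rises from 73.8% to 79.5%, and the whole gain comes from non-randomised subjects.

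**Do these figures apply to the confirmatory VAS tests?** Only if Protocol 5.6 overrides the definitions. Superiority uses ITT, which requires randomisation; non-inferiority uses a subset of ITT; the SAP tests only the comparative study. On those provisions the contrast stays at 43 v 43.

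**Do they apply to safety?** Here no Protocol definition excludes the pilot. Every device recipient is in the safety set, so the cap side is 15 + 43 = 58 with the same 26% share. If the pilot event rate differed by 10 percentage points (assumed), the pooled cap rate would move by 0.259 × 10 = 2.6 points. Read literally, Protocol 5.5.2 also contains no neurectomy-only subjects, so the comparison in 5.9 cannot be made from that set as worded. SAP 7.4.4 supplies the controls but does not split the phases.

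**The case against.** The strongest reply is that Protocol 5.6 fixes the timing of one final analysis after database lock, and then says only that pilot data accompany the comparative data. Joint reporting at a single lock is a fair reading. The population definitions and the SAP then do the rest for efficacy. This stands. A reader might infer that the randomised, blinded VAS comparison is broken as planned; the documents do not support that, because reaching 58 v 43 on the primary endpoint means setting aside Protocol 5.5.1 and 5.5.3 as well as SAP 7.4 and 9.1.2.

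A reader might also infer that the pilot data are used twice at a cost in error rate. The pilot objective is a single-arm 3-month change, summarised descriptively, and the available text shows no pilot-based gate or test. No such cost is shown.

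The size is also open to challenge. The shifts are assumptions and could favour either arm; some investigators may be new to the device (the bias-control measures before Protocol 3.7.1 provide for training them). The calculation uses raw means, whereas Protocol 5.7.4 plans a repeated-measures mixed model. The text of the hypotheses section is not available, so intent cannot be fully judged.

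On safety, SAP 8.1 read broadly would separate the phases there too, and SAP 9.3.2 plans summaries and listings without a between-group test. That softens the point but does not remove it: the between-group comparison and the success criterion are in the Protocol, where the safety set is not split.

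**Conclusion.** The concern holds as an unresolved contradiction with a bounded consequence. Protocol 5.6 conflicts with SAP 8.1 and fits poorly with the Protocol's own ITT and per-protocol sets. That finding rests on no assumption.

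For the confirmatory VAS tests the risk is conditional. The 26% share, the 0.26b bias and the raised type I error arise only if the 5.6 sentence is allowed to override the population definitions. Even the largest assumed shift gives 5.2 mm, below the 14-20 mm that the Protocol cites (as a reduction, not explicitly as a between-group difference), so the matter is one of validity and false-positive risk rather than a bias of clinical size.

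For safety the exposure is direct under the Protocol: pilot subjects belong to the set that feeds the between-group event comparison and, through it, the success decision. The direction and size of any distortion there are unknown.

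**What to change.** Replace the Protocol 5.6 sentence with:

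> Pilot and comparative phase data will be analysed separately. All between-group efficacy and safety comparisons, and the study success decision, use only subjects randomised in the comparative phase. Pilot results, and any pooled summary, are descriptive and labelled as such.

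Align Protocol 5.5.2 and SAP 7.4.4 so that the comparative safety set covers both randomised arms and pilot safety data are tabulated in their own column.

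The cost is a change of wording in both documents, handled as an amendment on the Protocol side (Protocol 12.1). The between-group safety comparison becomes 43 v 43 rather than 58 v 43, that is, 15 fewer cap subjects. Their events remain fully reported in the pilot column, and no extra data collection is needed.

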5.7 General Issues for Statistical Analysis

5.7.1 Multiple Comparisons and Multiplicity

All summaries of categorical data will be presented in frequencies and percentages. All summaries of continuous data will be presented by the number of non-missing values, mean, standard deviation, standard error, median, minimum, maximum, and coefficient of variation. Mann-Whitney U tests will be used to compare baseline data to ensure poolability across centers.

As the final data analysis is to be conducted using blinded group data, no adjustment for type I error is necessary for analysis. As the tests of non-inferiority and superiority are being performed in a closed testing procedure, there will be no adjustment for multiple secondary endpoints; a step-down procedure will be utilized in the assessment of the secondary efficacy endpoints:

- 1. VAS score at 1, 3, 6, 9 and 12 months compared to baseline
- 2. PROMIS® score at 1, 3, 6, 9 and 12 months compared to baseline
- 3. FHSQ score at 1, 3, 6, 9 and 12 months compared to baseline
- 4. Quantity, quality and class of pain medication use at 1, 3, 6, 9 and 12 months compared to baseline

Quantity class of pain medication used for end-neuroma pain

Rate of recurrence of symptomatic neuroma

For this procedure, the hypotheses will be tested sequentially based on the specified ordering. Statistical testing will continue at the =0.05 level until a p-value greater than 0.05 is observed.

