Amendment Date:

Axogen Corporation

Axoguard® Nerve Cap

PROTOCOL

A Multicenter, Prospective, Randomized and Subject Blinded Comparative Study of Axoguard® Nerve Cap and Neurectomy for the Treatment of Symptomatic Neuroma and Prevention of Recurrent End-Neuroma Pain

Protocol No. CAP-CP-001

CONFIDENTIAL - PROPRIETARY INFORMATION

Development Phase:	Pilot Cross-over to Comparative Parallel Group
Sponsor:	Axogen Corporation [name]
Sponsor Representative:	
Immediately Reportable Adverse Event:	Clinical Safety
V 3.0	
Issue Date:	27 Aug 2018

This clinical investigation will be performed to compliance with the protocol, the FDA Good Clinical Practices including 21 CFR part 50, 56, ICH E6, ISO 14155:2011 and local applicable regulatory requirements. This document is a confidential communication of Axogen, Corp. Acceptance of this document constitutes agreement by the recipient that no unpublished information contained herein shall be published or disclosed without prior written approval, except that this document may be disclosed to the appropriate Institutional Review Boards under the condition that they keep it confidential.

01 Mar 2021

Title of Study: A Multicenter, Prospective, Randomized, Subject Blinded Comparative Study of Axoguard[®] Nerve Cap and Neurectomy for the Treatment of Symptomatic Neuroma and Prevention of Recurrent End-Neuroma Pain

Estimated Number of Study Centers and Countries: Up to 20 Centers in the US

Study Type: Pilot to Comparative Parallel Group

Study Design: Randomized, controlled, prospective, subject blinded, multi-center, pilot to comparative parallel group study

Objective: The primary objective of the pilot phase of this study is to evaluate the difference in pain scores from baseline at 12 weeks; The primary objective of the comparative phase is the differences in pain assessments between the study groups at 12 months. The secondary objectives of this study are to compare degree of recovery over time (reduction in pain); quality of life and economic data for each treatment group over a 12-month period.

Study Population: Adult male and female subjects with symptomatic neuroma in the foot or ankle to at least one nerve where the nerve cannot be repaired to a distal nerve end

Test Product: Axoguard® Nerve Cap

Control: Neurectomy

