5.2 Statistical Analysis Plans

A statistical analysis plan (SAP) will be created and approved prior to the beginning of subject enrollment. This document will provide a more technical and detailed description of the proposed data analyses and statistical methods.

Test of non-inferiority and superiority of Axoguard® Nerve Cap compared to neurectomy with respect to VAS (visual analog scale) pain score will be conducted using closed testing procedures.

5.4 Sample Size Estimates A total of 101 subjects at up to 10 sites may be enrolled to control for site effects
For the pilot study, 15 evaluable subjects will first be selected to receive the open label Axoguard® Nerve Cap.
For the comparative study, 86 evaluable subjects will then be selected for enrollment.

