5.7.3 Planned Subgroups

5.7.4 Missing Data

Every effort will be made to obtain the required data at each scheduled evaluation from all subjects who have been randomized. In assessing the primary efficacy endpoint, a repeated measures mixed model will be utilized on all observed data.

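### Mann-Whitney tests on baseline data cannot show that 10 or 20 centres are poolable, and they do not address whether the treatment difference varies by site

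*Protocol*

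**What the plan says.** The protocol gives one poolability method, in the synopsis under Statistical Methods and again in 5.7.1: "Mann-Whitney U tests will be used to compare baseline data to ensure poolability across centers". The readable text does not say which baseline variables are tested, whether centres are compared in pairs or each against the rest, how multiplicity is handled, what result would mean that centres are not poolable, or what would follow.

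Other relevant statements:

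- **Number of centres.** The synopsis has "Up to 20 Centers in the US", and SAP 7.1 has "A total of 101 participants (15 pilot; 86 comparative/randomized) at up to 20 sites will be enrolled". Protocol 5.4 has "A total of 101 subjects at up to 10 sites may be enrolled to control for site effects".
- **Sample size.** Protocol 5.4: "For the comparative study, 86 evaluable subjects will then be selected for enrollment".
- **Test level.** Protocol section 5 sets the default: "all statistical testing will be two-sided and will be performed using an overall significance (alpha) level of 0.05".
- **Allocation.** SAP 7.2: "participants will be centrally randomized 1:1 to one of two treatment groups". No stratification by centre is stated.
- **Primary model.** Protocol 5.7.4: "In assessing the primary efficacy endpoint, a repeated measures mixed model will be utilized on all observed data". No site term is named. SAP 9.1.2 plans non-inferiority and superiority tests and names neither a model nor a site term.

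The readable SAP mentions neither poolability nor Mann-Whitney tests.

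**The concern.** There are three difficulties.

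1. The tool is a two-sample test and the problem has 10 or 20 samples. It can be applied only through a scheme of many tests, and none is given.
2. At the expected site sizes, individual comparisons have little power, while a full set of uncorrected comparisons produces frequent false alarms. The check could therefore be read either way.
3. It asks the wrong question. Pooling matters for the treatment difference, and centres with the same baseline can still differ in the effect of the procedure. For VAS, agreement at baseline is also partly built in, because eligibility restricts subjects to roughly 65 to 100 mm.

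Variation between sites is plausible. SAP section 4 leaves neurectomy to each institution's standard of care, and the protocol's bias measures allow investigators with prior Nerve Cap experience alongside those with in-service training only. At stake are a poolability statement in the report that the data cannot support and, if site is left out of the model, possibly some lost precision.

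**Working it through.** The documents give no figure for poolability, so there is none to reproduce. What follows is what the stated method would deliver.

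**Inputs.** 86 randomised subjects (Protocol 5.4); 10 sites (Protocol 5.4) or 20 (synopsis, SAP 7.1); two-sided 0.05 (Protocol section 5). Assumption: near-equal sites, that is 14 sites of 4 and 6 of 5 at 20 sites, or 4 sites of 8 and 6 of 9 at 10 sites.

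**Step 1: number of tests.** Pairs of k sites = k(k − 1)/2. For k = 20: 20 × 19/2 = 190 per baseline variable. For k = 10: 10 × 9/2 = 45. Average site size: 86/20 = 4.3 or 86/10 = 8.6.

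**Step 2: false alarms when all centres are identical.** Simulation of one continuous baseline variable, 1,000 trials per setting, each test at 0.05 uncorrected:

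| Scheme | 10 sites | 20 sites |
|---|---|---|
| At least one p < 0.05, all pairs (exact test) | 0.609 | 0.825 |
| At least one p < 0.05, each site against the rest | 0.376 | 0.602 |
| One Kruskal-Wallis test over all sites | 0.039 | 0.025 |

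With all 101 subjects instead of 86, the all-pairs figures are 0.591 and 0.86. Several baseline variables would offer further chances of a false alarm.

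**Step 3: power of one pair.** For a true baseline shift of 1 SD (normal data, 5,000 runs): 0.13 for 4 v 4, 0.22 for 5 v 5, 0.43 for 9 v 9.

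**Step 4: would a correction rescue it?** The smallest two-sided exact p is 2/C(n1 + n2, n1). For 4 v 4 this is 2/70 = 0.029, for 4 v 5 it is 2/126 = 0.016, and for 5 v 5 it is 2/252 = 0.008. Bonferroni over 190 pairs requires 0.05/190 = 0.00026, so at 20 near-equal sites no corrected pair could ever reject. At 10 sites the level is 0.05/45 = 0.0011, which is attainable (8 v 9: 0.00008), but at less than the power in step 3.

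**Step 5: does a baseline test see treatment-effect variation?** The true effect was varied between centres, with between-centre SD 0.5 or 1.0 of the outcome SD, and baselines were generated identically (1,500 runs). The baseline Kruskal-Wallis test rejected in about 3% (20 sites) to 4% (10 sites) of trials, which is its error rate with no heterogeneity. This holds by construction: baselines carry no information about the effect unless the two are linked. A treatment-by-site F test on the outcome had this power:

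| Between-centre SD of effect | 10 sites | 20 sites |
|---|---|---|
| 0.5 outcome SD | 0.27 | 0.16 |
| 1.0 outcome SD | 0.75 | 0.57 |

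The outcome-based test addresses the right question but is too weak to act as a gate, except where heterogeneity is very large.

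**The case against.** The best defence is that little hangs on this sentence. No endpoint, population or success criterion depends on the test, and the SAP, which Protocol 5.2 makes the more detailed document, does not repeat it. The all-pairs scheme in the working is an assumption; each site against the rest is also possible. The bias measures require fellowship training and procedure experience or instruction, which should narrow differences between surgeons. These points stand and limit the weight of the concern, but they do not make the method capable of what it claims: each site against the rest still gives a false alarm in about 38% to 60% of trials with identical centres.

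A reader might infer more than the documents support:

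- **That a non-significant result is guaranteed.** It is not. Power per pair is low, but over all pairs at least one significant result is more likely than not.
- **That many pairs could never reach 0.05.** This needs unequal sites with pairs as small as 3 v 4 (2/35 = 0.057). With near-equal sites of 4 and 5, every pair can reach 0.05 before correction.
- **That the intended control for site effects is absent.** This cannot be established. Protocol 5.7.2 (Covariates) is cut off mid-word, 5.7.3 shows no text, and SAP 9.1.2 breaks off in mid-sentence. Protocol 5.4 also ties site effects to enrolment and does not promise a model term.

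**Conclusion.** The concern holds for the stated method. Mann-Whitney tests on baseline data cannot establish poolability across 10 or 20 centres. Run over all pairs without correction, they would raise a false alarm in about 61% to 83% of trials with identical centres, while a single 4 v 4 pair would miss a 1 SD shift about 87% of the time (1 − 0.13). Neither outcome says whether the treatment difference varies by site. The figures assume near-equal sites and a continuous baseline variable without ties; the conclusion is the same at either site count.

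The consequence is moderate. The sample size is unaffected. It would be tempting to add that leaving out site biases the comparison, but with central 1:1 randomisation it does not do so by itself. The harm is a misleading check and possible loss of precision, whose size cannot be stated because the readable text gives no between-site variance. Whether the primary model has a site term remains open. The conflict between 10 and 20 sites is a separate consistency point and adds no weight to this one.

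**What to change.** 1. Delete the Mann-Whitney poolability sentence from the synopsis and from Protocol 5.7.1.
2. Include site as a random intercept in the primary repeated-measures VAS model, with small sites pooled by a rule fixed before unblinding. State the same model in SAP 9.1.2, which names none in its readable text. If a site term already exists in text not visible here, confirm it.
3. Assess poolability by a descriptive display of the treatment difference by pooled site, with confidence intervals. Do not use a gatekeeping test, since its power would be low (working, step 5). The display is needed as well as the intercept, because a random intercept alone does not show whether the effect varies by site.
4. Separately, give one site number in the synopsis, Protocol 5.4 and SAP 7.1.

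**Cost.** One variance component, which may be estimated near zero; one table or figure; a pooling rule; and alignment of the SAP model with the protocol. No new data should be needed. By-site estimates will be imprecise: before pooling, about 4.3/2 = 2.2 subjects per arm per site at 20 sites, or 8.6/2 = 4.3 at 10.

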3.5.2 Efficacy Endpoints

Primary Efficacy Endpoints

- 1. The change in VAS score at 3 months compared to baseline (pilot phase)
- 2. The change in VAS score at 12 months compared to baseline (comparative phase)

Secondary Efficacy Endpoints

- 1. The change in VAS score at 1, 3, 6, 9 and 12 months compared to baseline
- 2. The change in PROMIS® score at 1, 3, 6, 9 and 12 months compared to baseline
- 3. The change in FHSQ score at 1, 3, 6, 9 and 12 months compared to baseline
- 4. Changes in pain medication use at 1, 3, 6, 9 and 12 months compared to baseline
- 5. Rate of recurrence of symptomatic neuroma within 12 months

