5.8 Efficacy Analyses

5.8.1 Primary Efficacy Endpoint

The primary efficacy endpoint for both the pilot and comparative studies will be the change of VAS score at 3 months compared to baseline for subjects in both the Axoguard® Nerve Cap study arm and the neurectomy control arm.

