5.10 Study Success

Study success is defined as demonstrating the reduction in pain by VAS score with the treatment of Axoguard® Nerve Cap is superior to the reduction in VAS score for neurectomy group

In addition, there should be no clinically significant difference of product related adverse events rates following implantation of Axoguard® Nerve Cap compared to neurectomy.

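### Protocol 5.7.1 opens the secondary step-down at its own 0.05 without requiring primary superiority, and SAP 8.2/9.2.1 drops error control altogether, so an overall 0.05 does not cover secondary claims

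*Protocol*

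**What the plan says.** Protocol 5 states: "Unless specified otherwise, all statistical testing will be two-sided and will be performed using an overall significance (alpha) level of 0.05". The comparison of the two arms on VAS is to be made by closed testing of non-inferiority and superiority (Protocol 5.2, SAP 9.1.2). Protocol 5.10 ties study success to superiority on VAS plus an adverse-event condition; no secondary endpoint enters it.

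Protocol 5.7.1 gives the multiplicity rule. Its first reason for not adjusting is "As the final data analysis is to be conducted using blinded group data, no adjustment for type I error is necessary for analysis". It then cites the closed procedure and continues: "there will be no adjustment for multiple secondary endpoints; a step-down procedure will be utilized in the assessment of the secondary efficacy endpoints". The list begins with VAS at Months 1, 3, 6, 9 and 12, followed by PROMIS, FHSQ, pain medication and recurrence. On mechanics it says "For this procedure, the hypotheses will be tested sequentially based on the specified ordering", each step at 0.05, stopping at the first p-value above 0.05.

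The SAP, written against Protocol version 3.0, has no step-down. Section 8.2 states that type I error will not be controlled. Section 9.2.1 lists six secondary endpoints, each compared between arms, with no order and no condition on the primary.

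The primary time point is not settled within the Protocol. Section 3.5.2 and SAP 9.1.1 give Month 12 for the comparative phase, while Protocol 5.8.1 says "The primary efficacy endpoint for both the pilot and comparative studies will be the change of VAS score at 3 months compared to baseline".

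**The concern.** A step-down controls error within the family it orders. For the same 0.05 to cover the primary as well, the sequence must start only after the primary has been rejected. In 5.7.1 the only stop is internal to the secondary list, and the primary time point appears last among the visits of the first item, so it does not act as a gate.

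Neither stated reason fills the gap. Blinding the group data does not change how often true null hypotheses are rejected. A closed test of non-inferiority and superiority protects those two hypotheses and passes no alpha to other endpoints.

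At stake is the status of secondary findings after a failed primary. As written, the trial could miss its success criterion and still declare secondary endpoints significant at a fresh 0.05.

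**Working it through.** **Inputs.** Two-sided alpha of 0.05 (Protocol 5). Each secondary step at 0.05, stopping at the first failure (Protocol 5.7.1). Primary comparison: change in VAS at Month 12 (Protocol 3.5.2, SAP 9.1.1). First step: Month 1 VAS, the first visit listed in item 1. The correlation *r* between the primary and first-step test statistics is not in the documents, so it is an assumption and a range is shown. All results are for no true difference on any endpoint.

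**The plan's own figure.** The primary alone gives 0.05. The step-down alone, in strict order, also gives 0.05, because a false claim needs the first step to be rejected. Across both families, 0.05 is recovered if the step-down opens only after the primary is rejected: every false secondary claim then comes with a false primary claim.

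**The rule as written (no gate).** P(at least one false claim) = P(|Z₁| > 1.96 or |Z₂| > 1.96) = 0.05 + 0.05 − P(both). At *r* = 0 this is 1 − 0.95² = 0.0975. Other values are from the bivariate normal:

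| *r* | Primary or secondary false claim | False secondary claim with failed primary (total − 0.05) |
|---|---|---|
| 0 | 0.0975 | 0.0475 |
| 0.3 | 0.0951 | 0.0451 |
| 0.5 | 0.0907 | 0.0407 |
| 0.7 | 0.0835 | 0.0335 |
| 0.9 | 0.0704 | 0.0204 |
| 1 | 0.0500 | 0 |

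A simulation of one million draws per correlation agrees (0.0979, 0.095, 0.0907, 0.0835 and 0.0706 for *r* from 0 to 0.9). The gated rule gave 0.0497 to 0.0502 throughout.

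**Sensitivity to the order within item 1.** The order of visits inside the item is implied by the list rather than stated.
- If Month 12 VAS were tested first, with the same analysis and population as the primary, it would act as the gate and the total would be 0.05.
- If success at any of the five visits let item 1 pass, the total would be 1 − 0.95⁵ = 0.226 at *r* = 0, 0.18 at 0.5 and 0.15 at 0.7.

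**The SAP as written.** One primary and six secondary tests, each at an assumed 0.05 with no order: 1 − 0.95⁷ = 0.30 if independent. By simulation with equal pairwise correlation it is 0.27 at 0.3, 0.23 at 0.5 and 0.18 at 0.7.

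**The case against.** - **Missing text.** Protocol 5.3, Hypotheses Tested, is in the contents list but its text is not visible, and H₀B is used in 5.5.1 without a visible definition. A gate could sit there. This stands as a limit on certainty. However, 5.7.1 is the multiplicity section, states its procedure and reasons in full, and contains no gate.
- **No clear promise of 0.05 across both families.** The alpha statement in Protocol 5 allows exceptions, and 5.7.1 says no adjustment is needed. So a reader cannot hold the plan to an unambiguous commitment. The reasons given for the exception are still wrong.
- **The SAP may govern.** If it does, the step-down will not be run, the figures for it describe an analysis that will not happen, and a gate in 5.7.1 alone changes nothing. This stands, and is why the fix has to cover both documents.
- **Limited consequence.** Study success does not depend on any secondary endpoint, Protocol 5.8.2 speaks of descriptive summaries for the secondaries, and the SAP describes a post-market study. This also stands.

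Two stronger readings are tempting. A reader might infer that the trial's error rate is about 0.09. That single value needs an assumed correlation near 0.5 and Month 1 VAS as the first step, and the documents supply neither a correlation nor an explicit visit order. A reader might also infer that the primary conclusion is compromised. It is not: the primary superiority test keeps its 0.05.

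**Conclusion.** The concern holds for secondary claims. On the visible text, Protocol 5.7.1 gives the secondary sequence its own 0.05 whether or not the primary succeeds, and its two reasons for making no adjustment do not support that. With Month 1 VAS first and no true effect, the chance of a false claim somewhere across primary and secondary tests lies between 0.05 and 0.0975: 0.095 to 0.084 at assumed correlations of 0.3 to 0.7, and 0.070 at 0.9. With a gate it is 0.05. If any visit can carry item 1, it could be higher.

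The larger problem is that the two documents disagree. The SAP's unordered tests give about 0.18 to 0.30 at correlations of 0.7 to 0. The SAP openly disclaims control, so this is a conflict to resolve rather than a miscalculation.

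Non-inferiority would not serve as the gate. It is compatible with no difference between arms, and it is not the success criterion in 5.10. How often an ineffective cap would pass it cannot be computed, because no margin or standard deviation is visible.

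**What to change.** Reconcile Protocol 5.7.1 with SAP 8.2 and 9.2.1 on one rule and one ordered list of secondary endpoints. Delete the two rationale sentences in 5.7.1 and state in both documents:

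> Secondary endpoints are tested in the fixed order only if superiority on the primary endpoint (change in VAS at Month 12) is shown at two-sided 0.05. Non-inferiority alone does not open the sequence. Otherwise all secondary p-values are nominal and descriptive.

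This wording can be adopted only once Protocol 5.8.1 is aligned with Protocol 3.5.2 and SAP 9.1.1 on the primary time point. Remove Month 12 VAS from the secondary sequence, since it is the gate, and write out the order of visits and scales within each item. If Protocol 5.3 already contains a gate, cite it in 5.7.1 and carry it into the SAP.

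The cost is wording only; no data collection or sample size changes. The downside is that no secondary endpoint can be declared significant if primary superiority fails. All secondary results can still be reported with confidence intervals.
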